1.0 Background & Rationale

Some estimates suggest that by 2050, as many as 3.6 million people in the United States will be living with limb loss, and if historical trends continue, at least 60% of them will have had at least a foot removed [1]. For military personnel, combat-related amputations remain one of the most common major disabling war-related injuries from modern armed conflict. The return-to-duty (RTD) status of these Service members following amputation depends on the severity of injury, treatments rendered, and regenerative rehabilitation. Adequate rehabilitation post-amputation enables our nation's heroes to reach their maximum functional recovery and independence [3].

Technological advancements in active prosthetic devices for individuals with transtibial amputation offer the potential for superior function in key areas that could lead to higher rates of RTD and improved quality of life. Currently intended primarily for individuals with a K-level of 3 or 4, (This means the person can walk most environmental barriers possibly with variable cadence and some could have more than basic walking ability that could include the ability to do athletic activities) active transtibial prostheses that provide controlled plantar/dorsiflexion in either swing (microprocessor-controlled prostheses) or late stance (prostheses with powered propulsion) are likely to become the gold standard in the future as technology continues to improve [4]. Indeed, users of these types of prostheses have higher mobility than those using any of the other four categories of prosthetic ankle-foot mechanisms for unlimited community ambulators [5].

The PROPRIO FOOT® by Ossur is a microprocessor-controlled prosthesis that regulates the angle of ankle dorsiflexion during the swing phase. This added ankle control reduces the risk of falls by increasing toe clearance [6, 7], supports more natural standing posture on slopes [8, 9], and improves stair and slope ascent/descent capability by adapting to the change in terrain. These improvements also contributed to higher interlimb symmetry [12, 14, 15], reduced energetic cost of slope ascent [16], and higher Amputee Mobility Predictor with a Prosthesis (AMPPRO) scores [17].

The Empower ankle by Ottobock is a powered prosthesis that provides active propulsion in late stance to mimic the positive work performed by the ankle plantar-flexors in push-off. The Empower has been shown to improve affected leg kinematics (increased ankle range of motion and reduced knee flexion) on smooth flat ground [18], ramp ascent [19], and gravel [20]. The kinetic properties of Empower translate into increased affected ankle and whole leg work [23] and can produce higher self-selected walking speeds by increasing both step length and cadence [18, 24, 25]. However, the impact on interlimb symmetry is somewhat mixed, with peak ground reaction force [26,27] and leg work [28] asymmetries improving, while others remain [18, 22]. Overall, the relationship between the power setting of the device and performance characteristics can vary considerably with subject [29].

Interlimb symmetry is a focus because individuals with transtibial amputation who have used a prosthesis for several years experience a higher incidence of osteoarthritis in the intact leg [30],

osteoporosis in the affected leg [31], and other musculoskeletal problems. Residual limb tissues were not designed to tolerate the loads associated with supporting an individual's weight, so elevated socket loading can result in skin problems such as pressure sores [33, 34] and abrasions [35, 36]. The patellar tendon and the distal end of the fibula are known to be the most and least load-tolerant regions, respectively [37, 38]. In general, dissatisfaction with prosthesis comfort remains high [32, 39] due to the prevalence of skin sores or irritation within the socket [40].

The most common quantitative measure of prosthetic fit is pressure inside the socket during locomotion activities, and a wide range of measurement techniques have been pursued [41, 42]. Results show that mediolateral pressures tend to be less than anterior and posterior pressures, with anterior pressures typically being the highest [43]. Walking on slopes and stairs is of particular interest since internal stresses are known to be elevated in these cases [44] and pressure in level-ground walking is a poor predictor of that in these more challenging circumstances [45]. In stair ascent, the highest pressures are located in the proximal region of the anterior surface [46, 47], whereas they shift to the distal region with stair descent [47]. Gait and Motion Analysis is of particular interest to understand how a participant's gait can affect the amount of pressure that they place on their residual and intact limb. Beyond these activity-specific results, socket pressure has also been shown to be influenced by the type of suspension [43, 46], the type of foot [48, 49], and the alignment of the prosthesis [50–54].

Measuring fit via socket pressure, though, remains one step removed from limb health, the actual quantity of interest. More direct measures of limb health include transepidermal water loss (TEWL) for quantifying the functional integrity of the skin and laser speckle imaging (LSI) for quantifying skin perfusion. The PI's prior work has shown that, like socket pressure, TEWL is affected by the type of suspension (Fig. 3), but perfusion is not necessarily (Fig. 4) [62]. No studies to date have examined the effects of active lower-limb prostheses, neither micro-controlled nor powered, on these direct measures of limb health.

Active prostheses like the PROPRIO FOOT® and Empower ankle offer great potential to more completely restore the locomotor capabilities of individuals with transtibial amputation, perhaps enhancing RTD for military personnel. As with all prosthetic components, though, these active devices are of little use if they induce pain and/or injury at the residual limb to the degree that the user will simply not wear them. Overall, this project seeks to understand and quantify the effects of powered transtibial prostheses on socket loading and direct measures of residual limb health so as to inform the optimization of prosthesis fit.

2.0 Objective(s)

2.1 Primary Objective

Use of the powered Empower ankle prosthesis to determine differences in socket pressures compared to both the microprocessor-controlled PROPRIO FOOT® and a user's standard passive prosthesis for level-ground walking, stair ascent, and ramp ascent.

2.2 Secondary Objective

Obtaining quantitative measures of limb health, transepidermal water loss (TEWL) and skin perfusion, to identify differences among the use of the Empower ankle, the PROPRIO FOOT®, and an individual's standard passive prosthesis.

3.0 Outcome Measures/Endpoints

3.1 Primary Outcome Measures

Determine the effects of a powered transtibial prosthesis on the socket pressure for level-ground walking, stair ascent/descent, and ramp ascent/descent in comparison to a microprocessor-controlled prosthesis and a passive prosthesis at 4 weeks.

3.2 Secondary Outcome Measures

Determine the relative impact on residual limb health of the use of a powered prosthesis, a microprocessor-controlled prosthesis, and a passive prosthesis for individuals with transtibial amputation at 4 weeks.

- Transepidermal water loss (TEWL) measurements at 4 weeks
- Skin perfusion measurements and analysis at 4 weeks
- PEQ, CLASS and Comfort Score responses at 4 weeks

4.0 Eligibility Criteria

4.1 Inclusion Criteria

- Ages 18 and above
- Weight \leq 280 lb
- Ambulate at a K3 level or higher-level determined from patient EHR (Electronic Health Record)
- At least 3 months post-amputation per physician discretion
- Residual limb length greater than 4.5 inches
- Use of a passive prosthesis
- Unilateral transtibial amputees
- Must be able to ambulate without any assistive devices
- Subjects must be able to follow directions and give informed consent on their own

4.2 Exclusion Criteria

- Conditions and/or co-morbidities that would prevent wearing a prosthetic socket, affect gait, or influence function of the contralateral limb
- Amputees other than Unilateral transtibial

- Cognitive deficits or mental health problems that would limit ability to consent and participate fully in the study protocol
- Women who are pregnant or who plan to become pregnant in the near future
- Individuals undergoing dialysis and/or those with significant persistent fluctuations in residual limb volume
- Participants unwilling to wear a cloth face covering for the duration of each visit
- Must not have an active wound or scarring

5.0 Study Design

Participants will have the option to choose to attend 4 or 6 study visits. The number of visits participants decide to choose is based on subject preference depending on preferred time allocation. If opting for 4 study visits, visit 3 and 4 will be combined, as well as visit 5 and 6. The total time per participant to complete all visits will remain the same despite which option is chosen.

Randomization: Upon completion of study visit 1/ evaluation the subject will be randomized to initially receive either the PROPRIO FOOT® or the Empower ankle. A licensed prosthetist will fit the subject with the designated device at study visit 2 and establish the control settings per manufacturer recommendations and complete an alignment. The alternate device will be fitted at study visit 4.

Study Visit 1/Evaluation: This initial visit will take place at IU Health Methodist Hospital. Subjects will need to be evaluated to see if they are candidates for a prosthetic foot. They will need to undergo a clinical evaluation prior to determining eligibility, examining limb length and MPT-to-floor measurements. Additionally, for women participants of childbearing potential, attestation is required stating participant is not currently pregnant, nor planning to become pregnant and the date of their last menstrual period. Once subject is deemed to be a candidate, the following research activities will take place.

- Informed consent and HIPAA (if not previously completed)
- Research personnel will administer Socket Comfort Score questionnaire and PEQ-13 survey and CLASS survey
- Body weight recorded.
- Non-invasive limb health measurements performed (TEWL and Laser Speckle Imaging (LSI))
- Randomization
- Licensed prosthetist will perform pre-fitting and adjustments on the patient, ensuring the research foot (Foot A) will be ready to deliver during participant's next visit

Study Visit 2/Baseline: The subject's second visit will take place at the Noyes Pavilion of IU Health Methodist Hospital (Noyes). Study Visit 2 will occur within a week after Visit 1 with a window of 0-7 days. Participants will be asked to wear fitting shorts/athletic wear for visits held at Noyes prior to attending this visit. Study team members will offer specific guidance on style if necessary. The following procedures will be performed during this visit:

- Digital shape capture
- Administer pressure sensors inside participant's standard-of-care socket and initiate recording
- Body weight recorded.
- Multiple ambulation trials will be performed including level-ground walking tasks, stair ascent/descent tasks, and ramp ascent/descent trials
- 3D motion capture using the motion capture system will be conducted with the use of an electronic device that measures and reports a body's specific force, angular rate, and sometimes the orientation of the body, which are placed on subjects clothing to capture movement
Walking tasks and ascending/descending tasks on stairs and ramps will be completed with the use of force-sensing pads
- Timed get up and go test will be performed: subject will stand from seated position and walk 3 meters and then return and sit down
- Prosthetist will fit the participant with the research foot that was randomized to them
 - 15-30 minutes of usage of the prosthetic foot will be provided for acclimation
- Subject will repeat the level-ground, stair, and ramp trials with the new prosthetic foot (Foot A)
- Prosthetist will remove pressure sensors from the socket after ambulation and recording will be terminated

Upon completion of baseline, the subject will wear the research device (Foot A) for 4 weeks to become accustomed to the new technology through its exclusive use in place of their standard-of-care prosthetic foot.

Study Visit 3: After the four-week acclimation period, the subject will return for Visit 3 at IUH Methodist Hospital. A window of +/- 7 days will be implemented, ensuring the duration to complete Visit 3 remains consistent among all participants. The following activities will take place during Visit 3:

- Participant's weight will be captured
- Research personnel will administer surveys (Socket Comfort Score, CLASS and PEQ-13)
- Non-invasive limb health measurements performed (TEWL and Laser Speckle Imaging (LSI))

- Licensed prosthetist will perform pre-fitting and adjustments on the patient, ensuring the other research foot (Foot B) will be ready to deliver during participant's next visit

Study Visit 4 (Study Visit 3 if opted for 4 Study Visits): Study Visit 4 will occur within a week after Visit 3 with a window of 0-7 days. This visit will take place at Noyes. The following activities will take place:

- Digital shape capture will be performed
- Administer pressure sensors on participant's research socket and recording will be initiated using Foot A
- Body weight recorded.
- 3D motion capture using the motion capture system will be conducted with the use of an electronic device that measures and reports a body's specific force, angular rate, and sometimes the orientation of the body, which are reflective markers placed on subjects to capture movement
 - Level-ground, stair ascent/descent, and ramp ascent/descent trials will be completed with the device under the control settings established during Visit 1 (battery on)
 - Repetition of level-ground, stair ascent/descent, and ramp ascent/descent trials with the device's battery off
- Prosthetist will remove research foot (Foot A) from participant and fit with the other research foot (Foot B)
 - 15-30 minutes of usage of the prosthetic foot will be provided for acclimation
- Subject will repeat the level-ground, stair, and ramp trials with the new prosthetic foot (Foot B) with battery on
Prosthetist will remove pressure sensors from the socket after ambulation and recording will be terminated.
- Timed get up and go test will be performed: subject will stand from seated position and walk 3 meters and then return and sit down

Upon completion of study Visit 4, the subject will wear the research device (Foot B) for 4-weeks to become accustomed to the new technology through its exclusive use in place of their standard-of-care prosthetic foot.

Study Visit 5 (Final Visit if opted for 4 Study Visits): Study Visit 5 will occur at IUH Methodist Hospital, Comprehensive Wound Center Innovation Suite. A window of +/- 7 days will be implemented, ensuring the duration to complete Visit 3 remains fairly consistent among all participants. The following activities will take place during Visit 5:

- Participant's weight will be captured
- Research personnel will administer surveys (Socket Comfort Score, CLASS and PEQ-13)

- Non-invasive limb health measurements performed (TEWL and Laser Speckle Imaging (LSI))

Study Visit 6: Study Visit 6 will be the final visit which will occur within a week after Visit 5 with a window of 0-7 days. This visit will take place at Noyes. The following activities will take place:

- Digital shape capture will be performed
- Administer pressure sensors on participant's research foot (Foot B) and recording will be initiated
- Participant's weight will be captured
- 3D motion capture using the motion capture system will be conducted with the use of an electronic device that measures and reports a body's specific force, angular rate, and sometimes the orientation of the body, which are reflective markers placed on subjects to capture movement
 - Level-ground, stair ascent/descent, and ramp ascent/descent trials will be completed with the device under the control settings established during Visit 3 (battery on)
 - Repetition of level-ground, stair ascent/descent, and ramp ascent/descent trials with the device's battery off
 - Timed get up and go test will be performed: subject will stand from seated position and walk 3 meters and then return and sit down

Prosthetist will remove research foot (Foot B) from participant and recording will be terminated. At this point, the subject's participation in the study is complete, and the prosthetist will remove the pressure sensors from the socket, refit the subject's original standard of care prosthetic foot, evaluate alignment, and verify comfort for return to pre-study standard of care.

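### Minor: as listed, the Timed Up and Go is done once on the passive foot, twice on Foot B and never on Foot A; no entry names the foot, so the Visit 4 item may be misplaced.

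*Combined protocol and SAP*

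**What the plan says.** Section 5.0 lists a TUG at Study Visits 2, 4 and 6, and the calendar in Section 8.0 marks the same three visits.

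- **Visit 2.** The TUG is listed after the ambulation trials in the standard-of-care socket and before this step: "Prosthetist will fit the participant with the research foot that was randomized to them". Only the level-ground, stair and ramp trials are then repeated on Foot A.
- **Visit 4.** The list opens with "This visit will take place at Noyes. The following activities will take place". The Foot A trials come first, battery on and then off. Next come "Prosthetist will remove research foot (Foot A) from participant and fit with the other research foot (Foot B", 15-30 minutes of acclimation, and "Subject will repeat the level-ground, stair, and ramp trials with the new prosthetic foot (Foot B) with battery on". After that, "Prosthetist will remove pressure sensors from the socket after ambulation and recording will be terminated". The last item is "Timed get up and go test will be performed".
- **Visit 6.** The trials are on Foot B, battery on, followed by "ramp ascent/descent trials with the device's battery off". The TUG is next. Foot B and the sensors come off afterwards.

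None of the three TUG items names a foot or a battery state. Neither does the test description in Section 7.0 or the calendar row. TUG does not appear in the objectives (Section 2.0) or outcome measures (Section 3.0), and Section 13.0 does not name it. Section 13.0 says only in general terms that the three prostheses are compared within each subject on the measured quantities.

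**The concern.** One TUG at each of three visits, in a study of three prostheses, suggests one test per prosthesis. The listed order does not deliver that. By the time the Visit 4 TUG is reached, Foot A has been taken off and no step puts it back on, so the first-assigned device is never tested.

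The Empower versus PROPRIO FOOT comparison on TUG would then rest on Foot B alone. Participants whose Foot B is the Empower would be compared with participants whose Foot B is the PROPRIO FOOT, which is a between-sequence contrast and less precise than a paired one. The two Foot B tests are not simple replicates either, because the conditions around them differ. If staff do not treat the order as binding, the foot worn at the Visit 4 TUG could vary between participants without the record showing it.

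**Working it through.** The plan gives no figure for this point, so the check is a trace of the listed steps, followed by an illustration of precision.

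**Trace, taking the lists in order (Section 5.0)**

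| TUG at | Foot worn | Time on that foot | Sensors in socket | Battery state |
|---|---|---|---|---|
| Visit 2 | Passive (Foot A not yet fitted) | usual prosthesis | in | not applicable |
| Visit 4 | Foot B (Foot A removed, no refit) | 15-30 minutes of acclimation, plus the trials | out | not stated; preceding trials battery on |
| Visit 6 | Foot B (removed afterwards) | after the 4-week period | in | not stated; preceding trials battery off |

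Count per participant: passive 1, Foot A 0, Foot B 2. Tests with sensors in the socket: 2 of 3. TUG items that name the foot: 0 of 3.

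The shorter schedule does not change this: "If opting for 4 study visits, visit 3 and 4 will be combined, as well as visit 5 and 6". It merges visits without altering the order of the steps.

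If the Visit 4 TUG stood before the swap, the count would be passive 1, Foot A 1, Foot B 1, with both research feet tested after their wear periods. Within-subject Empower versus PROPRIO FOOT pairs per participant would go from 0 to 1.

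**Precision, illustrative only.** Assumptions not in the documents: N participants split equally between sequences, equal variance s² on every foot, and a common correlation r between a participant's TUG times.

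- Paired contrast (after the change): variance 2s²(1-r)/N.
- Foot B between-sequence contrast, unadjusted: s²/(N/2) + s²/(N/2) = 4s²/N. Ratio to paired: 2/(1-r).
- The same, adjusted for the passive TUG with known slope: 4s²(1-r²)/N. Ratio: 2(1+r).
- With the slope estimated: ratio 2(1+r) × [1 + 1/(N-4)]. The last factor is 1 + 1/16 = 1.0625 at N = 20 and 1 + 1/6 = 1.167 at N = 10.

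| Variance relative to paired | r = 0.5 | r = 0.8 | r = 0.9 |
|---|---|---|---|
| Unadjusted | 4 | 10 | 20 |
| Adjusted, known slope | 3.0 | 3.6 | 3.8 |
| Adjusted, estimated slope, N = 20 | 3.19 | 3.83 | 4.04 |
| Adjusted, estimated slope, N = 10 | 3.50 | 4.20 | 4.43 |

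A simulation of the estimated-slope case (200,000 runs per cell) gave 3.19, 3.82, 4.05 at N = 20 and 3.47, 4.18, 4.41 at N = 10, which agrees with the formula.

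**The case against.** The strongest reply is that the lists are not a chronology. At Visit 2, motion capture is listed after the ambulation trials it must record. Randomization is said to follow completion of Visit 1, yet the Visit 1 list puts it ahead of the pre-fitting. The calendar marks one TUG at each of the sessions that open on the passive foot, Foot A and Foot B, and at Visit 6 the test is grouped with the trials of the foot being worn. One test per prosthesis is therefore a plausible intent, and what is left is an unlabelled item. It can also be said that sensors come out after ambulation, which might include the TUG; that nothing in the documents shows sensors affect the test; and that no TUG comparison is specified, so none is lost.

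Much of this stands. The count of 1, 0 and 2 is one reading, not a proven design fact. The sensor difference is a secondary point. The variance ratios rest on assumed values for a contrast that the plan never spells out. The reply does not remove the problem, though. The Visit 4 steps depend on one another (swap, acclimate, repeat the trials, remove the sensors) and read naturally as a sequence. If the order is not binding, the foot worn at the Visit 4 TUG is undetermined, and the same correction is needed.

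**Conclusion.** The point holds, at minor weight. Followed as listed, the plan gives no TUG on Foot A and no within-subject Empower versus PROPRIO FOOT pair for this test, contrary to the general aim in Section 13.0. If the order is not meant literally, the text leaves the foot unspecified. The precision loss shown above, roughly three- to four-fold in variance with adjustment and 4- to 20-fold without, depends on the assumed r and N and is not needed for the conclusion. TUG is not a listed outcome, and the pressure, TEWL, perfusion and survey comparisons are not affected.

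**What to change.** In Section 5.0:

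- **Visit 4:** place the TUG directly after the Foot A battery-on trials, before Foot A and the sensors are removed.
- **Visit 6:** place the TUG directly after the Foot B battery-on trials, so that the two tests are comparable.
- **All TUG items, and the description in Section 7.0:** name the foot worn and the battery state.

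Each participant then has one TUG on the passive foot and one on each research foot after its wear period, all three with sensors in the socket. If an early Foot B value at Visit 4 is wanted, keep it as an extra, separately labelled test.

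The cost is a minor protocol revision. Either the early Foot B test is given up and the total stays at three TUGs per participant, or one short test is added and the total becomes four.
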